APPENDIX D: RESPONSE CRITERIA

Response and progression will be evaluated in this study using modified Prostate Cancer Working Group 2 criteria [43].

Evaluation of Target Lesions

Complete Response (CR):	Disappearance of all target lesions. Lymph node CR is when the lymph node has decreased to less than 10mm in the short axis.
Partial Response (PR):	At least a 30% decrease in the sum of the longest diameter (LD) of target lesions, taking as reference the baseline sum LD.
Progressive Disease (PD):	At least a 20% increase in the sum of the LD of target lesions, taking as reference the smallest sum LD recorded since the treatment started (including the baseline scan if that is the smallest), and at least a 5mm increase or the appearance of new lesions.
Stable Disease (SD):	Neither sufficient shrinkage to qualify for PR nor sufficient increase to qualify for PD, taking as reference the smallest sum LD since the treatment started.

Evaluation of Non-Target Lesions

Complete Response (CR)	Disappearance of all non-target lesions and PSA level <0.04 (undetectable)
Incomplete Response/Stable Disease (SD)	Persistence of one or more non-target lesion(s) and/or of PSA ≥ 0.04 but no increase $\geq 25\%$ over baseline and to at least PSA >2 ng/mL
Progressive Disease (PD):	Appearance of one or more new lesions and/or unequivocal progression of existing non-target lesions. . PSA increase by $\geq 25\%$ over baseline and to at least PSA >2 ng/mL . However, unequivocal progression should not normally trump target disease status. It must be representative of overall disease status change, not a single lesion increase

Although a clear progression of “non-target” lesions only is exceptional, the opinion of the treating physician should prevail in such circumstances.

Evaluation of Best Overall Response

The best overall response is the best response recorded from the start of the treatment until disease progression/recurrence (taking as reference for progressive disease the smallest measurements recorded since the treatment started). The patient's best response assignment will depend on the achievement of measurement criteria, but confirmation is not necessary.

Target Lesions	Non-Target Lesions	New Lesions	PSA	Overall Response
CR	CR	No	<0.04	CR
CR	Non-CR/Non-PD	No	Decline by >50% from baseline –pre ADT	PR
PR	Non-PD	No	Decline by >50% from baseline –pre ADT	PR
SD	Non-PD	No	No increase by 25 % over baseline and to a value of >2 ng/dL	SD

Target Lesions	Non-Target Lesions	New Lesions	PSA	Overall Response
PD	Any	Yes or No	Any	PD
Any	PD*	Yes or No	Any	PD
Any	Any	Yes	Any	PD
Any	Any	Any	increase by 25 % over baseline and to a value of >2 ng/dL	PD

*In exceptional circumstances, unequivocal progression in non-target lesions may be accepted as disease progression. Patients with a global deterioration of health status requiring discontinuation of treatment without objective evidence of disease progression at that time should be reported as “*symptomatic deterioration*”. Every effort should be made to document the objective progression even after discontinuation of treatment.

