- Must have at least 1 bone lesion **AND** each non-visceral lesion should be less than 5 cm
- Visceral lesions will be limited to one lung lesion (< 2cm) or one lymph node; no liver lesions allowed. Lymph nodes allowed provided they are not in a field of prior radiation, and if amenable to SBRT (to be reviewed by PI). (note: locoregional recurrence is not considered a “visceral metastatic lesion”. This is discussed more below)
- Two lesions can be in close proximity (i.e. within 5cm of each other) if they meet radiation SBRT normal tissue toxicity requirements
- *If have untreated primary prostate cancer:* Must undergo debulking prostatectomy at discretion of treating urologist or definitive radiation therapy. Definitive radiation fields to include close proximity lymph nodes at discretion of treating radiation oncologist. Definitive radiation dose at discretion of treating radiation oncologist.
- If had prior treatment to the prostate primary (definitive radiation therapy or prostatectomy, and can include salvage radiation to the prostate bed +/- lymph nodes), no evidence of locally persistent or recurrent prostate cancer on digital rectal exam (DRE) OR imaging studies (CT or MRI).
 - Note: patients with asymptomatic low volume locoregional recurrent disease will be allowed to enroll on this study after discussion with the PI. In the case where the low volume recurrence is amenable to SBRT, it will be included in the SBRT treatment. In the case where the low volume recurrence is not amenable to SBRT based on reirradiation risk, then we will follow these lesions with re-imaging scans and reassess at later time points for further local control. Additionally, if these patients fail only at the untreated site (due to the untreated recurrence not being amenable to SBRT) they will be censored in the primary efficacy analysis at that time.
- Does not have castration resistant disease (i.e. testosterone >50 ng/dl)

- PSA ≥ 0.2 prior to start of androgen deprivation treatment (ADT)
- Patients will be receiving approximately 36 weeks of ADT as part of this trial. The 36 weeks of ADT may start prior to consenting to this study. The patient may join the study at any point of the 36-week period of ADT treatment. .

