12.0 ENDPOINT EVALUATION CRITERIA/MEASUREMENT OF EFFECT

12.1 Efficacy Endpoints

Response and progression will be evaluated in this study using modified Prostate Cancer Working Group 2 criteria [43] (see [Appendix C](#) and [Appendix D](#)). PSA levels will be a part of overall response assessment. Other clinical efficacy endpoints are described in [Table 12.1](#).

Table 12.1 Efficacy Endpoints

Endpoint	Definition
Time to treatment failure (TTF)	Time from the initiation of ADT for metastatic disease until PSA increase to > pre-ADT level or PSA >10 (whichever is smaller) or radiographic or clinical progression or resumption of ADT by physician's choice
Objective response rate (ORR)	Proportion of patients achieving CR or PR at Cycle 8 Day 1 (post-6 doses of radium Ra 223 dichloride)
Complete response (CR) rate	Proportion of patients achieving CR
Progression-free survival (PFS)	Time from the initiation of ADT for metastatic disease until PSA progression or radiographic progression or death
Bone specific progression-free survival (Bs-PFS)	Time to progression of bone specific disease over baseline
Duration of response (DOR)	Time from documented response to recurrent or progressive disease is first met
Duration of overall complete response	Time from documented CR to recurrent/ progressive disease
Duration of stable disease	Time from start of treatment until the criteria for progression are met, taking as reference the smallest measurements recorded since the treatment started.
Overall Survival (OS)	Date of initiation of protocol treatment to date of death from any cause

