APPENDIX C: DISEASE PARAMETERS AND METHODS FOR EVALUATION

Response and progression will be evaluated in this study using modified Prostate Cancer Working Group 2 criteria [43].

Disease Parameters

- **Measurable disease:**

Measurable lesions are defined as those that can be accurately measured in at least one dimension (longest diameter to be recorded) as >10mm with conventional techniques (CT, MRI, or caliper measurement) and as >20mm by chest X-ray (if clearly defined and surrounded by aerated lung.) Lymph nodes greater than 15mm on short axis are considered measurable as well. All tumor measurements must be recorded in millimeters (or decimal fractions of centimeters).

- **Non-measurable disease:**

All other lesions (or sites of disease), including small lesions (longest diameter <20 mm by chest X-ray or <10 mm using CT, MRI or caliper measurement), are considered non-measurable disease. Organomegaly, leptomeningeal disease, ascites, pleural/pericardial effusions, lymphangitis cutis/pulmonis, inflammatory breast disease, and abdominal masses (not followed by CT or MRI) are all non-measurable.

- **Target lesions:**

All measurable lesions up to a maximum of 2 lesions per organ and 5 lesions in total, representative of all involved organs, should be identified as target lesions and recorded and measured at baseline. Lymph nodes less than 15mm in the short axis cannot be used as target lesions. Target lesions should be selected on the basis of their size (lesions with the longest diameter) and their suitability for accurate repeated measurements (either by imaging techniques or clinically). A sum of the longest diameter (LD) for all target lesions will be calculated and reported as the baseline sum LD. The baseline sum LD will be used as reference by which to characterize the objective tumor response.

- **Non-target lesions:**

All other lesions (or sites of disease) including any measurable lesions over and above the 10 target lesions should be identified as non-target lesions and should also be recorded at baseline. Measurements of these lesions are not required, but the presence or absence of each should be noted throughout follow-up.

Methods for Evaluation of Measurable Disease

All measurements should be taken and recorded in metric notation using a ruler or calipers. All baseline evaluations should be performed as closely as possible to the beginning of treatment and never more than 30 days before the beginning of the treatment.

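### Appendix D states the nodal size rule for complete response only in the target-lesion table, so a non-target node that shrinks further can be denied CR, or scored differently by different assessors

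*Combined protocol and SAP*

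**What the plan says.** Appendix C sorts nodes by short axis. On measurability it says: "Lymph nodes greater than 15mm on short axis are considered measurable as well". On target status it says: "Lymph nodes less than 15mm in the short axis cannot be used as target lesions". All remaining lesions or sites of disease are non-target, and for these: "Measurements of these lesions are not required, but the presence or absence of each should be noted throughout follow-up".

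Appendix D then gives separate CR rules.

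- Target table: all target lesions must be gone, with one nodal provision: "Lymph node CR is when the lymph node has decreased to less than 10mm in the short axis".
- Non-target table: "Disappearance of all non-target lesions and PSA level <0.04 (undetectable". No nodal provision follows. The next row, incomplete response or stable disease, applies on "Persistence of one or more non-target lesion(s) and/or of PSA" at or above 0.04.
- Overall table: CR needs target CR, non-target CR, no new lesions and PSA below 0.04. Target CR with a non-target result of non-CR/non-PD is PR, given a PSA fall of more than 50% from the pre-ADT value.

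Nodal disease is within the study population. The Synopsis and Section 3.1 (item 8) state: "Visceral lesions will be limited to one lung lesion (< 2cm) or one lymph node; no liver lesions allowed". Table 5.3 includes a nodal SBRT schedule.

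Table 12.1 defines the CR rate as "Proportion of patients achieving CR" and lists duration of overall complete response. Both are secondary objectives in Section 1.2.

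**The concern.** The two tables hold the same kind of lesion to different standards, depending only on which side of 15 mm it started. A node just above the cut needs only to fall below 10 mm. A node just below it must, on the literal text, be gone. A man with less nodal disease at entry, more shrinkage and a smaller residual node can therefore be placed in the worse category.

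The wording also leaves room for two readings. The nodal sentence sits under the target heading but speaks of lymph nodes in general. One assessor may confine it to targets, and another may apply it throughout. In a single-arm, open-label trial with 24 evaluable men, a CR definition that depends on the reader makes the CR rate hard to reproduce or to compare with other series.

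Small nodes are foreseeable. Section 2.1 explains that men with lower PSA are now admitted because imaging detects oligometastatic disease at lower PSA levels.

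**Working it through.** The plan gives no figure to reproduce. The check applies the rules of Appendices C and D to two men who differ only in the node. In both, all other lesions are gone, there are no new lesions and PSA is below 0.04.

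**Inputs.** Target cut at 15 mm short axis (Appendix C); nodal CR below 10 mm short axis (Appendix D, target table); non-target CR by disappearance (Appendix D, non-target table); pre-ADT PSA of at least 0.2 (Section 3.1, item 13); 24 evaluable patients (Section 13.3).

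| Step | Man A | Man B |
|---|---|---|
| Baseline short axis | 16 mm | 14 mm |
| Status under Appendix C | above 15 mm, can be a target | below 15 mm, must be non-target |
| Follow-up short axis | 9 mm | 5 mm |
| Decrease | (16 − 9)/16 = 43.8% | (14 − 5)/14 = 64.3% |
| CR row that applies | target: 9 < 10, met | non-target: still visible, not met |
| Category on the literal reading | CR | incomplete response/SD |
| Overall response | CR | not CR |

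**Man B's overall category.** If he also had a target lesion that disappeared, he is PR. The PSA condition for PR is met: a fall from 0.2 to 0.04 is (0.2 − 0.04)/0.2 = 80%, and a higher starting value or lower final value gives a larger fall. He then still counts in the objective response rate. If he had no target lesion, the overall table has no row that fits him.

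**The other reading.** If the nodal sentence is taken to cover all nodes, 5 < 10 and Man B is CR. The same scan and the same PSA yield two answers.

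**Can another passage settle it?** Appendix C asks only whether each non-target lesion is present or absent. No section gives a size at which a non-target node counts as absent or normal.

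**Size.** One reclassified man changes the CR rate by 1/24 = 0.0417, or 4.2 percentage points.

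**The case against.** The strongest reply is that the nodal sentence never uses the word target. It can be read as a general definition that happens to sit in the first table, and an assessor could record a 5 mm node as absent. This stands in part. It defeats the claim that the protocol plainly requires every non-target node to vanish. It does not remove the problem, because the sentence appears under the target heading, the non-target table has its own unqualified CR row, and no threshold for absence is given. Two reasonable assessors can still differ.

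A second reply is that the practical effect is small, and this also stands. Overall CR requires PSA below 0.04 and every other lesion gone, including the bone lesion that eligibility demands. Only a man who meets all of that and keeps a visible non-target node below 10 mm changes category. The CR rate carries no stated hypothesis or threshold, and a stricter CR rule errs on the conservative side.

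A reader might nevertheless infer a large loss of CRs. If 20% to 40% of men had a nodal metastasis and half of those nodes were under 15 mm, 24 × 0.20 × 0.5 = 2.4 to 24 × 0.40 × 0.5 = 4.8 men would be involved, or 10 to 20 points of CR rate. The documents do not support this. Neither share appears in them, and the product counts every man with a small node as a CR lost to the rule, so even under those shares it is a ceiling and not an estimate.

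A reader might also infer that duration of overall CR is understated. That is not shown. Duration runs from documented CR to recurrence or progression, so the rule changes who contributes, with no evident direction for the duration itself.

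**Conclusion.** The inconsistency is real and minor. On the literal text, the CR standard for a node depends on its baseline size in a way that can reverse the clinical ordering. On the alternative reading the reversal goes away, but the text does not say which reading applies.

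The effect is limited to the CR rate and to membership of the duration-of-CR analysis. It amounts to 4.2 percentage points of CR rate per reclassified man, on 24 evaluable patients. How many men that involves cannot be computed, because the documents do not give the share with a node under 15 mm or the share of those who meet every other condition for CR. Time to treatment failure does not use CR and is unaffected.

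The conclusion rests on two things: that a metastatic node under 15 mm is followed as a non-target lesion, which Appendix C implies, and that a node still visible at 5 mm has not disappeared.

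**What to change.** Keep the non-target CR row, including PSA below 0.04, and add one clause after the disappearance requirement: *a non-target lymph node of 10 mm or more in short axis at baseline counts as resolved when its short axis is below 10 mm.* Nodes already below 10 mm at baseline keep the present disappearance rule; otherwise they would satisfy the size rule at entry.

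This uses the protocol's own threshold and makes clear how it applies to both kinds of node. Man B becomes CR (14 ≥ 10 at baseline, 5 < 10 at follow-up), and Man A is unchanged. A boundary remains at a baseline of 10 mm, since smaller nodes must still disappear.

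Cost: an amendment to Appendix D, with a matching exception in Appendix C, because non-target nodes would need a short-axis reading at baseline and follow-up. That reading is not now required, but it uses scans already taken and adds no visits or imaging. The change should be made before response data are analyzed.

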The same method of assessment and the same technique should be used to characterize each identified and reported lesion at baseline and during follow-up. Imaging-based evaluation is preferred to evaluation by clinical examination when both methods have been used to assess the antitumor effect of a treatment

- **Clinical lesions:**

Clinical lesions will only be considered measurable when they are superficial (e.g., skin nodules and palpable lymph nodes). In the case of skin lesions, documentation by color photography, including a ruler to estimate the size of the lesion, is recommended.

- **Chest x-ray:**

Lesions on chest x-ray are acceptable as measurable lesions when they are clearly defined and surrounded by aerated lung. However, CT is preferable.

- **Conventional CT and MRI:**

These techniques should be performed with cuts of 10 mm or less in slice thickness contiguously. Spiral CT should be performed using a 5 mm contiguous reconstruction algorithm. This applies to tumors of the chest, abdomen, and pelvis. Head and neck tumors and those of extremities usually require specific protocols

- **Ultrasound (US):**

When the primary endpoint of the study is objective response evaluation, US should not be used to measure tumor lesions. It is, however, a possible alternative to clinical measurements of superficial palpable lymph nodes, subcutaneous lesions, and thyroid nodules. US might also be useful to confirm the complete disappearance of superficial lesions usually assessed by clinical examination

- **Endoscopy, Laparoscopy:**

The utilization of these techniques for objective tumor evaluation has not yet been fully and widely validated. Their uses in this specific context require sophisticated equipment and a high level of expertise that may only be available in some centers. Therefore, the utilization of such techniques for objective tumor response should be restricted to validation purposes in reference centers. However, such techniques may be useful to confirm complete pathological response when biopsies are obtained.

- **Tumor markers:**

Baseline PSA is defined as the last known PSA prior to the onset of ADT (anti-androgen or LHRH agonist/antagonist). PSA response criteria will be a part of overall response assessment and will also be recorded as a separate PSA response criteria. They are follows:

- PSA CR - PSA <0.04 confirmed at least 3 weeks later
- PSA PR - PSA decline by >50 % from baseline, confirmed at least 3 weeks later

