- PSA SD - PSA not meeting criteria for CR, PR or PD

- PSA PD - PSA increase by $\geq 25\%$ over baseline and to at least PSA >2 ng/mL confirmed at least 3 weeks later

- **Cytology, Histology:**

These techniques can be used to differentiate between partial responses (PR) and complete responses (CR) in rare cases (e.g., residual lesions in tumor types, such as germ cell tumors, where known residual benign tumors can remain).

The cytological confirmation of the neoplastic origin of any effusion that appears or worsens during treatment when the measurable tumor has met criteria for response or stable disease is mandatory to differentiate between response or stable disease (an effusion may be a side effect of the treatment) and progressive disease.

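### The Appendix D overall-response table gives the PSA progression floor in ng/dL and the other criteria give it in ng/mL, so men with pre-ADT PSA below 1.6 ng/mL are classified two ways

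*Combined protocol and SAP*

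**What the plan says.** Section 12.1 states: "Response and progression will be evaluated in this study using modified Prostate Cancer Working Group 2 criteria", and refers to Appendices C and D. Table 12.1 defines PFS as the time "until PSA progression or radiographic progression or death" and gives no separate PSA rule for PFS, duration of response or duration of stable disease. The appendices therefore have to supply it.

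The PSA progression floor is stated in these places:

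- Appendix C, tumor markers: a rise of at least 25% "over baseline and to at least PSA >2 ng/mL confirmed at least 3 weeks later".
- Appendix D, non-target lesions, stable-disease and progressive-disease rows: the same 25% rise, "over baseline and to at least PSA >2 ng/mL".
- Appendix D, overall response, stable-disease row: "No increase by 25 % over baseline and to a value of >2 ng/dL".
- Appendix D, overall response, last progressive-disease row: "increase by 25 % over baseline and to a value of >2 ng/dL". In this row the lesion columns may take any value, so PSA alone decides.

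On the reference value, Appendix C says: "Baseline PSA is defined as the last known PSA prior to the onset of ADT". The best-overall-response text in Appendix D, however, speaks of "taking as reference for progressive disease the smallest measurements recorded since the treatment started", and Table 12.1 uses the same kind of reference for duration of stable disease.

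TTF has its own PSA trigger in Table 12.1: a value above the pre-ADT level or above 10, whichever is smaller.

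**The concern.** The two units put the floors at 2 ng/mL and 0.02 ng/mL. The discrepancy sits in the table that converts lesion and PSA findings into an overall response, so it is an operative rule and not background text. Someone applying that table literally would call progression in men whom Appendix C calls stable on PSA.

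The men concerned are ones the trial now recruits on purpose. Inclusion criterion 13 admits a pre-ADT PSA of 0.2, and Sections 2.1 and 13.5 explain that the lower limit was introduced because imaging now detects disease at lower PSA and to help accrual. With 24 evaluable patients, a few reclassified men can visibly move a response rate or a median duration.

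A second, smaller ambiguity lies beside it. Every PSA progression criterion is written against baseline, while two of the definitions that use progression refer to the smallest value since treatment started. The documents do not say whether that wording covers PSA or only lesion measurements.

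**Working it through.** Inputs: the floors and the 25% rise (Appendices C and D); the pre-ADT reference (Appendix C); the lowest eligible PSA, 0.2 (Section 3.1, criterion 13, which gives no unit; ng/mL is assumed); the TTF trigger (Table 12.1). The plan states no figure of its own to reproduce here.

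**Unit.** 1 dL = 100 mL, so 2 ng/dL = 2/100 = 0.02 ng/mL.

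**Thresholds.** Let b be the pre-ADT PSA in ng/mL.

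- ng/mL wording: progression above max(1.25b, 2).
- ng/dL wording: progression above max(1.25b, 0.02).
- TTF trigger: min(b, 10).

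**Where each floor binds.** The ng/mL floor binds when 1.25b < 2, that is b < 1.6. The ng/dL floor binds when 1.25b < 0.02, that is b < 0.016, which no eligible man has. The two wordings therefore conflict only for b from 0.2 to below 1.6, and only while PSA lies between 1.25b and 2 ng/mL.

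| b | ng/mL wording | ng/dL wording | Ratio of the two | TTF trigger | ng/mL wording / TTF |
|---|---|---|---|---|---|
| 0.2 | 2.0 | 0.25 | 8 | 0.2 | 10 |
| 0.5 | 2.0 | 0.625 | 3.2 | 0.5 | 4 |
| 1 | 2.0 | 1.25 | 1.6 | 1 | 2 |
| 1.6 | 2.0 | 2.0 | 1 | 1.6 | 1.25 |
| 5 | 6.25 | 6.25 | 1 | 5 | 1.25 |
| 10 | 12.5 | 12.5 | 1 | 10 | 1.25 |
| 20 | 25 | 25 | 1 | 10 | 2.5 |
| 50 | 62.5 | 62.5 | 1 | 10 | 6.25 |

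**One patient.** Take b = 0.3 and a later PSA of 0.4. The 25% limit is 1.25 × 0.3 = 0.375, so 0.4 exceeds it. It also exceeds 0.02, so the overall-response table gives progressive disease. It does not exceed 2, so Appendix C gives PSA stable disease and the non-target table does not give progression.

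**Confirmation.** Appendix C asks for a second value at least 3 weeks later. The overall-response row does not, and Appendix D says that assigning best response needs no confirmation. The two routes to PSA progression therefore also differ in whether a single value is enough.

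**Reference value.** To size the baseline-or-smallest question, suppose the nadir is 0.2 ng/mL; Section 2.1 reports nadirs below that in 90% of the predecessor trial. A 25% rise over 0.2 is 0.25, so the 2 ng/mL floor would govern and progression would be called at 2 whatever b is. Against the pre-ADT baseline it is called at 12.5 for b = 10 and at 62.5 for b = 50.

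**Against TTF.** Since 1.25b > b, max(1.25b, 2) always exceeds min(b, 10). The last column gives the gap: 1.25-fold for b of 1.6 to 10, wider at both ends. In time this depends on the PSA doubling time, which the documents do not give. At an assumed 3 months, log2(1.25) = 0.32 doublings is about 1 month, and log2(6.25) = 2.64 doublings (b = 50) is about 8 months. Over an assumed range of 1 to 12 months, the b = 50 figure runs from 2.6 to 32 months.

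**The case against.** The strongest reply is that ng/dL is a typing slip. All the other statements of the rule say ng/mL, and a competent data reviewer would read it that way. That is very likely true, and it is why the correction is easy. It does not remove the problem, because the slip appears twice, in the table that assigns the overall category.

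The reply is also right about several stronger readings that a reader might infer:

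- *That progression thresholds differ 100-fold.* Only the floors do. The 25% condition takes over, so the thresholds differ at most 8-fold, and not at all from b = 1.6 upward.
- *That PSA progression is called far too late in general.* For b of 1.6 to 10 the gap to the TTF trigger is 1.25-fold, about 1 month at a 3-month doubling time and less than the 3-monthly PSA interval. The gap is large only at the extremes, and it concerns the PSA component alone: PFS also ends at radiographic progression or death, with imaging every 6 months and at PSA progression.
- *That PFS reaching its PSA limit after TTF is an error.* These are separately defined endpoints, and the pre-ADT baseline is stated explicitly. A pre-ADT reference may be deliberate, since PSA can rise as testosterone recovers after ADT stops at 36 weeks.
- *That one PSA rule should replace all of them.* Carrying the TTF trigger over to every endpoint would keep a pre-ADT reference for men at or below 10, would itself call 0.3 rising to 0.4 progression, and, if confirmation were added, would alter the primary endpoint during the trial against a fixed 16-month historical median. That is a debatable trade-off and not a correction.
- *That the primary endpoint is affected.* Section 13.5 paraphrases TTF with the words PSA progression, but Table 12.1 gives TTF its own PSA trigger, which contains neither floor.

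**Conclusion.** The overall-response table is wrong as written. Its PSA floor is 0.02 ng/mL where the rest of the document has 2 ng/mL. For a pre-ADT PSA from 0.2 to below 1.6 ng/mL, any PSA between 1.25 times that value and 2 ng/mL is progression by one table and not by the others. The discrepancy is greatest, 8-fold, at the entry limit and vanishes at 1.6. It bears on the secondary endpoints of PFS, response, duration of response and duration of stable disease. No sample-size or power figure depends on it.

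The unclear PSA reference is a secondary point that needs a sentence of clarification. The distance between the PSA progression threshold and the TTF trigger is a design feature worth a sensitivity analysis and does not call for a new rule.

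This rests on reading the entry PSA in ng/mL. The documents give no distribution of pre-ADT PSA, so the number of men in the conflicting range is unknown. The months quoted rest on assumed doubling times, and imaging may detect progression first.

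**What to change.** 1. In the Appendix D overall-response table, change ng/dL to ng/mL in the stable-disease row and in the last progressive-disease row.
2. Have that progressive-disease row refer to the Appendix C PSA rule, including its confirmation at least 3 weeks later, so that there is one definition of PSA progression for response and PFS.
3. State, for duration of stable disease (Table 12.1) and best overall response (Appendix D), whether the smallest-value reference covers PSA or only lesion measurements. If PSA stays against the pre-ADT baseline, say so there.
4. Leave the TTF definition and the main PFS rule as they are. Add a sensitivity analysis of PFS and duration of response that uses the Table 12.1 PSA trigger, above min(b, 10).
5. Check overall responses already recorded for men with pre-ADT PSA below 1.6 ng/mL, and reassign any that relied on the ng/dL floor.

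The cost is two table cells, two sentences and one extra analysis. PSA is already measured every cycle and about every 3 months in response follow-up, so no new data are needed.
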